3.4.4.1 Pregnancy testing

Pregnancy will be reported as an SAE. For women of child-bearing potential (WOCBP), pregnancy will be recorded in the subject's daily e-diary based on urine HCG pregnancy testing performed at site or at home. If a urine HCG test is positive, serum pregnancy testing will be performed by the central laboratory for confirmation. The study drug will be discontinued in subjects discovered to be pregnant at any time during the study.

3.4.5 Vital signs

Vital signs include blood pressure (BP) (mmHg) and heart rate (beats per minute). These measurements will be obtained at the time points indicated in the Appendix (Section 8.1).

3.4.6 Electrocardiograms

Electrocardiograms (ECGs) will be assessed during the lead-in visit, Week 26, Week 52, and, if applicable, during the ETD and Rescue visits. Overall evaluation of ECG is collected by visit as normal or abnormal, and the relevance of the abnormality is termed as “clinically significant” or “not clinically significant”. Any ECG finding that is judged by the investigator as a potentially clinically significant change (worsening) compared with the baseline value will be recorded as an AE.

3.4.7 Physical examinations

Complete and targeted physical examinations will be performed at the time points indicated in the Appendix (Section 8.1).

Abnormal findings prior to signing the informed consent will be recorded in the CRF in the medical history or AE pages depending on their onset date. Any physical examination finding that is judged by the investigator as a potentially clinically significant change (worsening) compared with a baseline value should be reported as AEs. No physical examination summaries will be presented.

3.4.8 Body weight, height and body mass index

Body weight and height will be measured at the time points indicated in the Appendix (Section 8.1). Body mass index (BMI) at each time point is derived from the actual weight (kg) divided by the actual height (m) squared measured at that time point. If either weight or height is missing at a given visit, no imputation of BMI will be performed.

In addition, the z-score adjusted for age and sex using Centres for Disease Control and Prevention (CDC) for normalised body weight, height and BMI will be derived at each time point.

Method of BMI calculation:

- Convert pounds (lb.) to kilograms ($\text{kg} = \text{lb.} / 2.2$),
- Convert inches (in) to centimetres ($\text{cm} = \text{in} \times 2.54$),
- $\text{BMI} = (\text{weight in kg}) / (\text{height in cm}/100)^2$,

Round to one decimal place (if 0.05 or greater, round up).

Normalised height, weight and BMI will also be summarised adjusted for age and sex and will be derived as z-score using CDC growth charts. Z-scores are calculated as:

$$Z = \frac{\left[\left(\frac{\text{value}}{M} \right) ** L \right] - 1}{S * L}$$

where:

- value = the child's height, weight or BMI;
- M, L and S correspond to values in the growth chart³ and vary according to the child's sex and age (months) or sex and height.

Details regarding age derivation are given in the Appendix (Section 8.6.1). For subjects ≥ 20 years old the normalised value will be based on the age of 239.5 months.

In addition, normalised BMI will also be presented using the following categories of percentiles: $\geq 95^{\text{th}}$ (refers to Obese), $\geq 85^{\text{th}}$ and $< 95^{\text{th}}$ (refers to Overweight), $\geq 5^{\text{th}}$ and $< 85^{\text{th}}$ (refers to Healthy Weight), and $< 5^{\text{th}}$ (refers to Underweight).

3.4.9 Measures of growth and maturity

Measures of growth and maturity include Tanner staging and central laboratory evaluations of growth and maturation markers and bone biomarkers. These will be assessed during the lead-in visit (Tanner staging only) or Day 1 prior to first dose (growth, bone and maturation markers only), and at Week 26, Week 52, Week 104, and (if applicable) at the ETD, Rescue and non-treatment follow-up visits.

Tanner staging is a measure of pubertal development rated on a scale of stage 1 to stage 5 (for details see Appendix Section 8.10.1). Tanner staging will be determined based on investigator assessment and the subjects' self-reports.

Growth and maturation markers

- Thyroid-stimulating hormone (TSH),
- Free thyroxine (assessed at Screening if TSH is abnormal),
- Luteinising hormone (LH) (females only),
- Follicle-stimulating hormone (FSH) (females only),
- Oestradiol (females only),
- Total testosterone (males only),
- Insulin-like growth factor-1 (IGF-1),
- Insulin-like growth factor binding protein-3 (IGFBP-3),
- Calcitonin,
- 25-hydroxy vitamin D.

Bone biomarkers

- Bone alkaline phosphatase,
- Osteocalcin,
- Parathyroid hormone (PTH),

- Carboxyterminal cross-linked telopeptide of Type 1 collagen (CTX-1).

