| Pregnancy Test (WOCBP only) | X | | X | X | X | X | X | WOCBP must have a negative serum or urine pregnancy test within 24 hours prior to the start of study drug. Home pregnancy kits will be provided. |

Table 5.1-2: Short-term Procedural Outline (CV181375 [D1680C00019])

| Procedure | Day 1ª | Wk 2 ^{a,b} | Wk 6 ^a | Wk 12 ^a | Wk 14 ^{a,c} | Wk 20 ^a | Wk 26/ETD (early discontinuation of IP)/Rescue ^{a,c} | Notes |
|---|-----------|------------------------|----------------------|-----------------------|-------------------------|-----------------------|--|---|
| Spot Urine Glucose | X | | X | X | | X | Х | Results blinded to the Sponsor, Investigator, site, and subject for the duration of the study following IP administration on Day 1 until after study completion |
| Growth, bone and maturation markers | X | | | | | | X | Thyroid-stimulating hormone (TSH), free thyroxine, luteinizing hormone (LH), follicle-stimulating hormone (FSH), estradiol, total testosterone, insulin-like growth factor-1 (IGF-1), insulin-like growth factor binding protein-3 (IGFBP-3), calcitonin, 25-hydroxy vitamin D, bone alkaline phosphatase, osteocalcin, parathyroid hormone (PTH) and carboxyterminal cross-linked telopeptide of Type 1 collagen (CTX-1) |
| Plasma samples for analysis of dapagliflozin, saxagliptin and 5-OH-saxagliptin ^d | | | X | X | | X | X# | Samples will be collected pre-dose and approximately 2 hours post-dose (± 1 hour) Samples will be drawn in the fasting condition. # No samples will be drawn at the Rescue Visit or the Week 26 Visit following Early Treatment Discontinuation Visit |
| Plasma samples for DPP-4 activity ^d | х | | X | Х | | Х | X | On Day 1 plasma samples for DPP-4 activity will be drawn pre-dose only. At the Weeks 6, 12, 20 and 26 visits, plasma samples for DPP-4 activity will be drawn at 2 hours (± 1 hour) post-dose only. Samples will be drawn in the fasting condition. |

Table 5.1-2: Short-term Procedural Outline (CV181375 [D1680C00019])

| Procedure | Day 1 ^a | Wk 2 ^{a,b} | Wk 6 ^a | Wk 12 ^a | Wk 14 ^{a,c} | Wk 20 ^a | Wk 26/ETD (early discontinuation of IP)/Rescue ^{a,c} | Notes | | | |
|---|-----------------------|------------------------|----------------------|-----------------------|-------------------------|-----------------------|--|---|--|--|--|
| Study Drug / IXRS | | | | | | | | | | | |
| Contact IXRS | X | | X | | X | X | X | | | | |
| First randomization | X | | | | | | | | | | |

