5.3.7 Measures of Growth and Maturity

Measures of growth and maturity will include Tanner staging and laboratory evaluations of growth, bone and maturation markers.

Tanner staging (Appendix 3) will be determined by Investigator assessment and subjects' self-reports.

Growth, bone and maturation markers will include:

- Thyroid-stimulating hormone (TSH) and free thyroxine
- Luteinizing hormone (LH), follicle-stimulating hormone (FSH), estradiol, and total testosterone
- Insulin-like growth factor-1 (IGF-1) and insulin-like growth factor binding protein-3 (IGFBP-3)
- Calcitonin, 25-hydroxy vitamin D, bone alkaline phosphatase, osteocalcin, and PTH
- Carboxyterminal cross-linked telopeptide of Type 1 collagen (CTX-1)

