8.4.3.1 Short-term and Long-term Assessment

The number and percent of subjects with at least one AE will be summarized for each treatment group, including summaries of AEs, SAEs, and AEs leading to discontinuation. Summaries will include the number of subjects with events by system organ class and preferred term. In addition, the proportion of subjects experiencing at least one episode of hypoglycemia during the 26 weeks of ST treatment and 52 weeks of treatment (ST+LT) will be summarized by treatment group.

The incidence of marked laboratory abnormalities through 26 weeks (ST), and separately, through 52 weeks (ST+LT) will be summarized for each treatment group.

Values and changes from baseline at each scheduled time point for clinical laboratory parameters, body weight and vital signs, including seated BP and HR, will be summarized by treatment group using descriptive statistics. The normality/abnormality of ECG tracings, as determined by the Investigator, will be summarized by shift tables overall and by ECG tracing at baseline. Tanner staging and measures of growth will also be summarized by treatment group using descriptive statistics.

The Treated Subjects Data Set will be used for all safety analyses, including data after rescue (primary safety analysis). Additional sensitivity analyses on data collected prior to rescue will be performed for AEs, hypoglycemia events, and clinical laboratory marked abnormalities. The primary analyses of events of hypoglycemia will be performed excluding data after rescue. Safety analyses will be performed using data from the ST treatment period (at the time of the primary endpoint analysis) and then again at the final database lock (52 weeks) on the combined ST+LT treatment period.

Measures of growth, bone, and maturation markers will be summarized for ST and the combined ST+LT treatment periods.

For these analyses, safety data will be summarized by treatment group based on the treatment received (dapagliflozin/saxagliptin/placebo) using the Treated Subjects Data Set.

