4.7.7.3 Growth and maturity markers

Summaries of growth and maturation markers (see Section 3.4.9) in SI and conventional units will be based on observed data, regardless of rescue medication initiation. Descriptive summaries of absolute values and changes from baseline (where applicable) will be provided for baseline, Week 26, Week 52, and for the post-study visit at Week 104 using the LOCF approach. For the Week 104 analyses, change from Week 52 will also be presented.

In addition, growth and maturation markers will also be summarised during the randomised withdrawal period using the Randomised Withdrawal Subjects Data Set for the first two treatment comparisons described in Section 4.1.5. Descriptive summaries of absolute values and changes from withdrawal baseline (where applicable) will be provided for withdrawal baseline, Week 52 and Week 104 using the LOCF approach.

A categorical change from baseline summary will also be produced by treatment group, age category (≥ 10 and < 15 years, ≥ 15 and < 18 years) using the randomisation strata, and puberty status at Week 26, Week 52 and Week 104 (as defined in Appendix Section 8.10.3) for Week 26, Week 52, and for the post-study visit at Week 104 using the LOCF approach. Similarly, a categorical change from withdrawal baseline summary will also be produced for the Randomised Withdrawal Subjects Data Set for Week 52 and Week 104 using the LOCF approach.

A listing of the growth and maturation markers along with the Tanner stages by subject will be provided. For the ST+LT period this listing will include all data collected up to the end of the LT period. For the ST+LT + Week 104 period, the listing will include all data collected up to Week 104.

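### LH and FSH are scheduled without a sex limit, but the SAP's marker list, and so its summary tables, restricts them to girls, and the departure is not declared

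*SAP*

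**What the plan says.** Protocol 5.3.7 names the reproductive hormones among the maturation markers as "Luteinizing hormone (LH), follicle-stimulating hormone (FSH), estradiol, and total testosterone". The notes to the marker row in the schedules of Protocol 5.1 repeat the list as "luteinizing hormone (LH), follicle-stimulating hormone (FSH), estradiol, total testosterone". No sex limit appears in either place. The row is marked at Day 1 and at Week 26 (Table 5.1-2), at Week 52 and Week 104 (Table 5.1-3), and in the follow-up after early treatment discontinuation (Table 5.1-4). The SAP's own schedules, Tables 14 to 16, carry the same unrestricted row.

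For the analysis, Protocol 8.4.3.1 states: "Measures of growth, bone, and maturation markers will be summarized for ST and the combined ST+LT treatment periods". It sets no sex limit.

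SAP 3.4.9 gives a sex-specific list. The entries are "Luteinising hormone (LH) (females only", "Follicle-stimulating hormone (FSH) (females only" and "Total testosterone (males only", each in brackets, and oestradiol is likewise limited to females. SAP 4.7.7.3 then points back to that list: "Summaries of growth and maturation markers (see Section 3.4.9) in SI and conventional units will be based on observed data".

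SAP Table 12, which records changes of analysis from the protocol, does not mention the restriction. Neither it nor 3.4.9 gives a reason.

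**The concern.** Protocol 1.3.3 makes growth and maturity a safety objective, followed for 52 weeks beyond the end of treatment, in a population aged 10 to below 18 years. LH and FSH are among the markers that the protocol chose for it. Under the SAP list, girls keep three reproductive hormones in the tables (LH, FSH, oestradiol) and boys keep one (testosterone). A protocol-specified safety marker is therefore dropped for one sex by a bracket in an endpoint list, with no stated reason and no entry in the table meant to record such departures. If the results exist, a drug-placebo comparison of LH and FSH in boys will not appear in any summary table.

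**Working it through.** The documents state no figure on this point, so the check is a comparison of texts plus a count of the subjects affected.

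**Text comparison**

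| Hormone | Protocol 5.3.7 and schedules; SAP Tables 14 to 16 | SAP 3.4.9, used by 4.7.7.3 |
|---|---|---|
| LH | no sex limit | females |
| FSH | no sex limit | females |
| Oestradiol | no sex limit | females |
| Total testosterone | no sex limit | males |

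1. Is the missing sex limit in the schedules informative? The same protocol schedule writes a restriction into the row label when it means one: "Pregnancy Test (WOCBP only", bracketed. The marker row has none, so its natural reading is all subjects. This is an inference. No sentence says that LH and FSH are assayed in boys.
2. Does the restriction reach the tables? Yes. SAP 4.7.7.3 takes its markers from 3.4.9, and both the descriptive tables and the categorical change tables by age and puberty status follow from it.
3. Is the departure declared? No. Table 12 records changes as small as adding a PK analysis set and combining the randomised withdrawal treatments in one table, but not this one.
4. Is the SAP consistent with itself? No. Its schedules and its section 3.4.9 disagree.

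**Subjects and results affected**

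Inputs: 243 randomised 1:1:1 (Protocol 3.1); the female share is held between one third and two thirds (Protocol 3.1), so the male share has the same bounds; four fixed visits with the marker row (Day 1, Weeks 26, 52 and 104).

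- Boys: 243 × 1/3 = 81, to 243 × 2/3 = 162.
- Per arm, if the sexes are balanced across arms: 81 / 3 = 27, to 162 / 3 = 54.
- Results per hormone at the four fixed visits: 81 × 4 = 324, to 162 × 4 = 648.

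The last range is a ceiling for those visits. It assumes that every boy is assayed and attends all four. Dropout, missed visits and the removal of site 4910 from the main tables (SAP 4.10) lower it. Samples at rescue or early-discontinuation visits are not counted.

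**The case against.** The strongest reply is that the bracket in SAP 3.4.9 may describe collection rather than summary. The section sits under endpoints and says when the markers are assessed. Another bracket in the same list, on free thyroxine, concerns when the test is done, and Protocol 5.3.7 lists free thyroxine without that qualifier too. On this reading boys' LH and FSH may never have been assayed, and no result is lost. The laboratory manual and the CRF would settle it, and neither is available here. The reply stands as far as it goes: assay in boys is not proved. It does not remove the conflict, because the protocol and SAP Tables 14 to 16 would then be wrong about what is measured.

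Four stronger readings might be inferred, and the documents support none of them.

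- *LH and FSH are drawn from every boy and discarded.* Assay in boys rests on an unrestricted panel row. A by-subject listing of the markers with Tanner stage is also planned in SAP 4.7.7.3, although it does not say whether boys' LH and FSH would appear.
- *Children give extra blood for an unused assay.* LH and FSH share one panel row with TSH, testosterone, IGF-1, IGFBP-3 and the bone markers, which boys need in any case. No additional draw is shown.
- *The maturity objective fails in boys.* Tanner stage, puberty status with height velocity, height and its z-score, IGF-1, IGFBP-3 and the bone markers are still summarised for them. Protocol 1.3.3 does not name LH or FSH.
- *Only boys are affected.* The same mismatch applies to testosterone in girls, as well as to oestradiol in boys.

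It could also be argued that a testosterone difference in boys cannot be interpreted without LH and FSH. The documents make no such argument, and these are descriptive group tables without hypothesis tests.

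**Conclusion.** The conflict is real and undeclared. As the SAP stands, any LH and FSH results from boys fall outside every summary table of maturation markers, and testosterone is the only reproductive hormone summarised for a group of 81 to 162 of 243 subjects. The 324 to 648 results per hormone are an upper limit for the fixed visits and depend on assay in boys, which the documents imply but do not state.

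The consequence is limited to descriptive safety summaries. Primary and secondary efficacy analyses are unaffected. It is still more than a wording slip, because a protocol-scheduled marker for a stated paediatric safety objective disappears from the tables for one sex without a reason. It should be settled.

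**What to change.** First establish from the laboratory manual and the CRF which of the four hormones are assayed in which sex.

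- **If LH and FSH are assayed in both sexes:** delete the female-only brackets after LH and FSH in SAP 3.4.9, and summarise both hormones by sex within treatment group in the existing 4.7.7.3 tables. The split by sex is needed because those tables are now laid out by treatment, age category and puberty status only. Treat oestradiol and testosterone consistently: either summarise them by sex as well, or declare the restriction and its reason in Table 12.
- **If boys' LH and FSH are not assayed:** reconcile Protocol 5.3.7, the protocol schedules and SAP Tables 14 to 16 with SAP 3.4.9, and record the change and its reason in Table 12.

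The cost is SAP wording and one extra stratum in planned tables, or a correction to the protocol text and schedules. Neither route needs new samples.

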3.5 Other variables

Other variables include demographics, diabetes-related and other baseline characteristics, randomisation stratification factors, exposure to rescue medication (insulin), and exposure and compliance to study medication.

3.5.1 Demographic and baseline characteristic variables

Demographics data are collected on or prior to first randomisation. For subjects that are rescreened, demographics data collected at re-screening will be used in the analysis.

Demographic and baseline characteristics are listed in [Table 5](#). Diabetes-related baseline characteristics are listed in [Table 6](#). Renal function baseline characteristics are listed in [Table 7](#).

Table 5 Demographic and Baseline Characteristics

Characteristic	Summarised as	Categories
Sex	Categorical	Male Female
Age	Categorical and Continuous	≥ 10 and < 15 years ≥ 15 and < 18 years
Race	Categorical	White Black or African American Asian Native Hawaiian or Other Pacific Islander American Indian or Alaska Native Other
Ethnicity	Categorical	Hispanic/Latino Non-Hispanic/Latino
Baseline Height (cm) and Normalised Height	Continuous	-
Baseline Body Weight (kg) and Normalised Weight	Continuous	-
Normalised BMI	Categorical and Continuous	Percentiles as defined by CDC* $\geq 95^{\text{th}}$ $\geq 85^{\text{th}}$ and $< 95^{\text{th}}$ $\geq 5^{\text{th}}$ and $< 85^{\text{th}}$ $< 5^{\text{th}}$
Geographic region	Categorical	Regions as defined in Appendix Table 22 Asia/Pacific Europe Latin America North America

* $\geq 95^{\text{th}}$ refers to *Obese*; $\geq 85^{\text{th}}$ and $< 95^{\text{th}}$ refers to *Overweight*; $\geq 5^{\text{th}}$ and $< 85^{\text{th}}$ refers to *Healthy Weight*; $< 5^{\text{th}}$ refers to *Underweight*.

Table 6 Diabetes-Related Baseline Characteristics

Characteristic	Summarised as	Categories
Duration of Type 2 Diabetes Mellitus (see below for calculation)	Categorical and Continuous	< 2 years ≥ 2 and ≤ 5 years > 5 years
HbA1c	Categorical and Continuous	< 6.5% ≥ 6.5 and < 8% ≥ 8 and $\leq 10.5\%$ > 10.5%
FPG	Continuous	
Background anti-diabetic medication	Categorical	Metformin only Insulin only Metformin + Insulin
Background anti-diabetic medication total daily dose	Continuous	Metformin dose Insulin dose
Combinations of randomisation stratification factors	Categorical	Male - ≥ 10 and < 15 years - Metformin only Male - ≥ 10 and < 15 years - Insulin only Male - ≥ 10 and < 15 years - Metformin + Insulin
		Male - ≥ 15 and < 18 years - Metformin only Male - ≥ 15 and < 18 years - Insulin only Male - ≥ 15 and < 18 years - Metformin + Insulin
		Female - ≥ 10 and < 15 years - Metformin only Female - ≥ 10 and < 15 years - Insulin only Female - ≥ 10 and < 15 years - Metformin + Insulin
		Female - ≥ 15 and < 18 years - Metformin only Female - ≥ 15 and < 18 years - Insulin only Female - ≥ 15 and < 18 years - Metformin + Insulin

Table 7 Baseline Renal Function Characteristics

Characteristic	Summarised as	Categories
eGFR	Categorical and Continuous	< 60 mL/min/1.73 m ² ≥ 60 and < 90 mL/min/1.73 m ² ≥ 90 and < 120 mL/min/1.73 m ² ≥ 120 mL/min/1.73 m ²

Total Daily Dose of Metformin or Insulin

If several medications are ongoing on Day 1, the doses will be summed.

Duration of diabetes

Duration of diabetes will be calculated as the number of years from T2DM diagnosis date to informed consent date:

$$(\text{Date of informed consent} - \text{date of T2DM diagnosis} + 1) / 365.25.$$

Rules for handling missing or partial T2DM diagnosis dates are provided in the Appendix (Section 8.4). Duration of diabetes, even if partially imputed, will be included in the relevant listing. Only observed dates will be presented in the listings.

3.5.2 Medical history

Medical history includes medical conditions with onset prior to the informed consent signature, that stopped prior to screening or were ongoing at screening. Medical conditions will be coded using the current version of MedDRA at the time of database lock to map each verbatim term to a SOC and PT.

3.5.3 Prior and concomitant medications

Information on all prior and concomitant medications and therapies will be reviewed throughout the study and at Week 56. Treatment details for subjects receiving background insulin and/or metformin will be recorded separately to other non-study medications. All medications will be coded using the current version (at the time of database lock) of World Health Organisation Drug Dictionary (WHO DD), and the Anatomical Therapeutic Chemical (ATC) classification system.

Medications will be classified as prior or concomitant. A prior medication is defined as any medication that started and stopped prior to the first randomised dose. Concomitant medications are those with either

- A recorded medication start date falling within the analysis period (ST or ST+LT treatment period), or
- A recorded medication start date prior to the first day of double-blind study medication without any recorded medication stop date prior to the start of the ST treatment period, or
- A recorded medication start date prior to the first day of ST study medication with a recorded medication stop date after the start of the ST treatment period.

Rules for classifying medications as prior or concomitant in case of partial, missing or invalid start and stop dates are described in the Appendix (Section 8.3). Only observed dates will be presented in the listings.

Antidiabetic concomitant medications will be selected using WHO-DD ATC coding:

- All insulin antidiabetic medication (A10A)
- All non-insulin antidiabetic medication (A10 but not A10A)

